2 STUDY OBJECTIVES

The objective of this protocol is to observe the safety of Replagal in Canadian patients with Fabry disease.

3 STUDY DESIGN

3.1 General Description

This is an open-label, single-arm, multicenter, Phase III/IV safety study and is designed to evaluate the safety of Replagal in Canadian patients with Fabry disease. All patients may continue to receive Replagal in this treatment plan until Replagal AF is commercially available for the patient, the patient's participation or the study is discontinued, whichever comes first. Safety data will be collected throughout the treatment protocol.

A minimum of 60 patients with Fabry disease and up to 200 patients are expected to participate in this protocol. Two cohorts are included in the protocol; Cohort 1 is for patients from the Canadian Fabry Disease Initiative (CFDI) and provides Replagal treatment on an every other week (EOW) regimen and cohort 2 is only for patients who participated in REP001a and provides Replagal treatment on a weekly regimen. Patients may begin to enroll in the treatment protocol as soon as the eligibility criteria are fulfilled and informed consent is obtained.

3.2 Discussion of Study Design, Including the Choice of Control Groups

This protocol is intended to follow the same schedule and assessments as the CFDI protocol, and the safety visits in this protocol are intended to coincide with the twice annual or annual visits recommended by the CFDI. This includes the collection of screening data which will be obtained up to 6 months prior to the patient's initiation of treatment with Replagal, to align with the patients' current biannual assessment schedule in the CFDI.

For patients in Cohort 1, Replagal will be administered at a dose of 0.2 mg/kg body weight as an intravenous (IV) infusion over 40 (\pm 10) minutes EOW (\pm 5 days).

For patients in Cohort 2, Replagal will be administered at a dose of 0.2 mg/kg body weight as an IV infusion over 40 (\pm 10) minutes weekly (\pm 2 days).

Based on the weights obtained at the biannual visits, or annual visits, as applicable, the dose should be updated if the weight change is \pm 5% from the initial weight or from the previous visit, or at the discretion of the investigator.

3.3 Method of Assigning Patients to Treatment Groups

This is a single-arm study, thus all patients will be assigned to one treatment group.

3.4 Method of Assigning Patients to Cohorts

Only patients who have participated in REP001a will be enrolled in Cohort 2 to receive weekly dosing with Replagal. All other patients will be enrolled in Cohort 1 to receive EOW dosing with Replagal.

3.5 Randomization and Blinding

This is an open-label study, thus neither randomization nor blinding will occur.

3.6 Determination of Sample Size

Health Canada requested that a minimum number of patients be specified in order to obtain meaningful safety data from this safety clinical trial. With a minimum of 60 subjects, there will be at least a 95% chance of observing at least one adverse event (AE) of a given type, if the event has a frequency of 5%.

4 EFFICACY AND SAFETY VARIABLES

4.1 Schedule of Evaluations

Complete schedules of events (SOE) for Cohort 1 and Cohort 2 are provided in [Appendix 1](#) and [Appendix 2](#). This protocol is intended to follow the same schedule and assessments as the CFDI protocol, and the safety visits in this protocol are intended to coincide with the biannual or annual visits recommended by the CFDI.

Patients enrolled in this study must be treated in accordance with current Canadian guidelines for the treatment of Fabry disease.

4.2 Primary Efficacy Endpoint

There is no primary efficacy endpoint in this study. The primary endpoint is safety as described in section [5.4](#).

4.3 Secondary Efficacy Endpoint

Not applicable

4.4 Safety Assessments

Safety and tolerability will be assessed by AE reporting, changes in vital signs (from immediately before to immediately after every infusion), and changes from screening assessments to biannual visits in physical examination, blood tests, and anti-agalsidase alfa antibodies (in serum).

4.5 Drug Concentration Measurements

Not applicable

5 STATISTICAL ANALYSIS

5.1 General Methodology

All analysis will be performed by the Biometrics Department, Shire HGT using SAS[®] Software version 9.3 or higher (SAS institute, Cary, NC, USA). All study data will be presented in by-patient data listings.

No formal statistical tests will be conducted. Tabular summaries of patient baseline demographic and clinical characteristics, patient disposition, medical history, vital signs, AEs, anti-agalsidase alfa antibody, and infusion information will be produced for the safety population. The safety population includes all patients who receive at least one full or partial infusion of Replagal. Continuous data collected prior to receiving study drug and at subsequent visits will be summarized using descriptive statistics (n, mean, median, minimum, maximum, and standard deviation). Categorical data will be summarized as frequencies and percentages. All data summaries will be presented for each cohort and overall, as appropriate, unless otherwise indicated

Cohort:

Cohort is defined as:

- Cohort 1: Patients from CFDI and receiving Replagal on EOW regimen
- Cohort 2: Patients who participated in REP001a and receiving Replagal on weekly regimen

Data Derivations:

The following key derived and computed variables have been initially identified. It is expected that additional variables may be required. The SAP will not be amended for additional variables. All derived and computed variables, including additional variables later identified, will be documented in the “Define Document,” and also in the SAS analysis dataset creation programs. The following are anticipated data derivations:

- *Screening period:* Within 6 months prior to first dose
- *Pre-treatment period:* Prior to first study drug infusion
- *Day 1:* Day of first study drug infusion
- *Date of Enrollment (entry):* Date informed consent is signed
- *Baseline:* Last valid non-missing assessment made prior to the first study drug infusion.
- *Change from Baseline:* Post-baseline value – Baseline Value

- *% Change from Baseline:* $\{(Change\ from\ Baseline / Baseline) * 100\}$
- *Change from Pre-infusion:* Value immediately after infusion – value immediately before infusion.
- *% Change from Pre-infusion:* $\{(Change\ from\ pre-infusion / pre-infusion) * 100\}$
- *Age:* integer of $\{(date\ of\ informed\ consent - date\ of\ birth) / 365.25\}$
- *Duration of study drug exposure:* (Date of last infusion – date of first infusion)+1
- *Descriptive statistics:* n, mean, standard deviation (SD), median, minimum (min), and maximum (max)

Handling of Outliers:

For analysis purposes an outlier is defined to be an observed value which is known to be the result of an obvious error, or an observed value beyond medical reasoning. No outliers will be excluded from any analyses. The analysis may be repeated, however, by excluding any potential outliers (i.e. a sensitivity analysis performed).

Missing Dates for Adverse Events:

For partial AE dates, the non-missing parts of the partial dates will be used to determine if an AE occurred prior to the first dose of Replagal. Unless the non-missing parts are *unambiguously* before or after the first Replagal, it will always be assumed that the AE occurred after the first Replagal dose.

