7.7 Sensitivity Analysis

For analysis purposes, an outlier is defined to be an observed value which is known to be the result of an obvious error, or an observed value beyond medical reasoning. No outliers will be excluded from the main analysis. A sensitivity analysis may be performed by excluding any potential outliers.

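### The SAP's outlier rule keeps values known to be errors in the main means, SDs, minima and maxima when they were not corrected before lock and have no valid repeat

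*SAP*

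**What the plan says.** SAP 5.1 (Handling of Outliers) gives a definition with two limbs: "an observed value which is known to be the result of an obvious error, or an observed value beyond medical reasoning". The rule that follows is "No outliers will be excluded from any analyses", and the next sentence adds "The analysis may be repeated, however, by excluding any potential outliers". SAP 7.7 repeats the definition, words the rule as "No outliers will be excluded from the main analysis", and continues "A sensitivity analysis may be performed by excluding any potential outliers".

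Two other SAP rules depend on validity:

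- In the SAP 5.1 derivations, baseline is the "Last valid non-missing assessment made prior to the first study drug infusion".
- In SAP 5.7.2, where a laboratory test is repeated at a visit, the second set is used unless it is invalid or missing. A first-set value then replaces it, provided that value is itself valid.

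The SAP does not define *valid*, and it does not say how these two rules relate to the outlier rule. SAP 5.7.3 has no repeat or validity rule for vital signs.

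**The concern.** Keeping extreme but possibly genuine observations is sound practice in a safety study. The first limb of this definition is different: it names values already known to be wrong, and the rule keeps them. No run without them is guaranteed, because both sections only permit one.

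The study has no formal tests. For laboratory data and vital signs the result is therefore the descriptive table: observed values and changes, shown by cohort, by previous ERT status and overall. The mean, SD, minimum and maximum are the statistics that one wrong number distorts most, and a column for a small cohort or ERT category would be the most exposed. A programmer also has no stated way to decide whether the outlier rule or the validity rules take precedence.

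**Working it through.** **Which values the rule reaches.** Take a recorded value that is recognised as wrong and follow it through the SAP, reading *valid* in its ordinary sense.

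| Situation | Governing text | Outcome |
|---|---|---|
| Corrected before lock | None needed | No longer an outlier |
| Pre-dose value, uncorrectable | Baseline definition, 5.1 | Passed over in favour of the last valid value |
| Laboratory value with a valid repeat at the same visit, at baseline or later | Retest rule, 5.7.2 | The valid value is used |
| Single post-baseline laboratory value, uncorrectable | Outlier rule, 5.1 and 7.7 | Kept |
| Vital sign other than the baseline value, uncorrectable | Outlier rule, 5.1 and 7.7 | Kept |

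The first three rows are protected and the last two are not. In rows two and three the outlier rule and the validity rules give opposite instructions, and the SAP does not say which wins. The scope also differs: 5.1 speaks of any analyses, although its next sentence allows a run with exclusions, while 7.7 speaks only of the main analysis.

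**The plan's own figure.** The only design figure is in SAP 3.6: at least a 95% chance of seeing an event of 5% frequency in 60 patients. It reproduces as 1 − 0.95^60 = 0.954. It does not depend on the outlier rule.

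**Size of one retained error.** The values n = 60 and n = 200 are the SAP's minimum and maximum enrolment. The values n = 10 and n = 20 are assumed, because the documents do not give the size of Cohort 2 or of the ERT categories. All means, SDs and errors below are also assumed.

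Let n − 1 correct values have mean m and SD s, and let one wrong value be x.

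- Mean with the error: M = ((n − 1)m + x)/n
- SD with the error: √{[(n − 2)s² + (n − 1)(m − M)² + (x − M)²]/(n − 1)}

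For a tenfold error in a typical value, x = 10m, so M = m(1 + 9/n). The mean rises by 900/n per cent: 90% at n = 10, 45% at n = 20, 15% at n = 60 and 4.5% at n = 200.

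Example: potassium with m = 4.2 and s = 0.4, and one value entered as 42.

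| n | Mean | SD | Maximum |
|---|---|---|---|
| 10 | 7.98 | 11.96 | 42 |
| 20 | 6.09 | 8.46 | 42 |
| 60 | 4.83 | 4.90 | 42 |
| 200 | 4.39 | 2.70 | 42 |
| Any, error removed | 4.2 | 0.4 | not affected by the error |

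At n = 60 the mean is (59 × 4.2 + 42)/60 = 4.83. A mean change from baseline moves by the same absolute amount, (42 − 4.2)/60 = 0.63.

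A milder error is a weight of 165 lb entered as kg, with m = 75 and s = 15. At n = 60 it gives mean 76.5 and SD 18.9. At n = 200 it gives mean 75.5 and SD 16.3.

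**What is little or not affected.** One post-baseline error misplaces at most one patient in a given shift table: 1/60 = 1.7%, 1/200 = 0.5%, or 1/10 = 10% in an assumed group of 10. The median barely moves. Counts of adverse events, serious events and infusion-related reactions do not use these values.

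**The case against.** The strongest reply is that the rule forbids exclusion, not correction, and that known errors should rarely reach the analysis. Protocol 6.19 provides for cross-checking case report forms against source, and Protocol 6.18 for documented corrections. Protocol 6.10.1.1 has out-of-range laboratory tests repeated until normal or explained. SAP 7.3 plans review meetings and cleaning before lock. A gross slip such as the potassium example is the kind most likely to be caught. All data are also listed by patient, so an absurd maximum can be traced. Much of this stands, and it makes the affected set small. It does not justify the sentence: if no known error survives cleaning, that limb of the rule does nothing, and if one survives, the rule puts it in the table. The laboratory repeat provision does not help vital signs, which are taken around each infusion, may be recorded at home, and cannot be measured again later.

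A second reply is that values beyond medical reasoning may be genuine, so keeping them is the cautious choice. That stands, and the criticism is limited to confirmed errors.

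A reader might infer that every known error is kept in all main summaries, or that only baseline is screened for validity. The documents do not support either reading. The baseline definition passes over invalid pre-dose values, and the retest rule applies at any visit with a repeat, including those after baseline.

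**Conclusion.** The point holds in a narrow form. The wording defect is certain: the SAP defines outliers to include known errors, keeps them in the main analysis, makes the alternative optional, and conflicts with its own validity rules. The effect on results is conditional. It needs an error that is recognised, not corrected before lock and without a valid repeat, and nothing in the documents shows how often that will occur.

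Where it does occur, the mean, SD, minimum and maximum are exposed. A tenfold error raises a mean by 15% at n = 60 and by 90% at n = 10, where the error and the group of 10 are assumptions. A reader might go further and infer that false safety signals are likely, or that real ones will be hidden. The documents do not establish this: medians are reported alongside, individual values are listed, shift tables change by one patient at most, and adverse event counts are unaffected. No test, error rate or power is involved. The rule should be corrected because it is wrong as stated and cheap to repair.

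**What to change.** Amend SAP 5.1 and 7.7 in the same words:

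- A value confirmed as an error by query or source check is corrected. If it cannot be corrected, it is set to missing in the main summaries and flagged in the listings. Each decision is documented before lock.
- Extreme or implausible but unconfirmed values stay in the main summaries. A sensitivity summary excluding them is produced whenever any exist.
- *Valid* is defined once and used with that meaning in the baseline definition, the laboratory retest rule and both outlier passages.
- The scope is stated identically in both sections, as the main analysis.

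The cost is a few sentences, one data flag and a short record of decisions. SAP 7.2 already leaves missing values unimputed outside partial dates and early-termination data, so a value set to missing simply lowers n by one. The one risk is added discretion to remove safety data in an open-label study. Requiring confirmation by query or source, and not by judgement of plausibility alone, limits it.

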6.10.4 Procedures for Recording and Reporting Adverse Events

6.10.4.1 Adverse Event Monitoring and Period of Observation

Adverse events will be monitored continuously throughout the study.

For the purposes of this study, the period of observation extends from the time at which the patient, the patient's parent(s), or the patient's legally authorized representative gives informed consent until the patient's final evaluation of the study. For safety purposes, the final evaluation will be defined as the follow-up evaluation performed approximately 30 days after the last dose for patients who complete the study.

If the investigator considers it necessary to report an AE in a study patient after the end of the safety observation period, he or she should contact the sponsor to determine how the AE should be documented and reported.

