5.7 Analysis of Safety

5.7.1 Adverse Events

Adverse events will be coded using the Medical Dictionary for Regulatory Activities (MedDRA) central coding dictionary, version 13.1 or higher, and will be tabulated by cohort, previous SRT status, age group and overall based on the safety population. .

Pre-treatment AEs are any AEs that occur from the time the patient has signed informed consent until prior to the first study drug infusion.

Treatment-emergent adverse events (TEAEs) will be defined as those events that occurred or worsened in severity after first treatment with Replagal AF until 30 days after the last dose.

Infusion-related reactions (IRRs) will be defined as an AE that 1) begins either during or within 12 hours after the start of the infusion and 2) is judged as possibly or probably

related to study drug. AEs that are considered IRRs will be noted as such in the appropriate field on the CRF.

A serious AE (SAE) is any AE occurring at any dose that results in any of the following outcomes:

- Death
- Is life-threatening
- Require hospitalization
- Requires prolongation of existing hospitalization
- A persistent or significant disability or incapacity
- A congenital anomaly or birth defect

Important medical events that may not result in death, be life-threatening, or require hospitalization may be considered an SAE when, based upon appropriate medical judgment, they may jeopardize the patient and may require medical or surgical intervention to prevent one of the outcomes listed in this definition.

TEAEs will be summarized by system organ class (SOC) and preferred term (PT). The total number of TEAEs by SOC and PT, as well as the number and proportion of patients experiencing a TEAE will be tabulated; a patient will be counted only once within each SOC and PT. TEAEs by SOC and PT will be tabulated by severity. In the case of multiple occurrences of the same TEAE (at the PT level) in an individual patient, the TEAE that is classified as the most severe (i.e., maximum severity) will be identified for the analysis by severity. In addition, TEAEs by SOC and PT will be tabulated by relationship to study drug by reporting the episode with the closest relationship to study drug.

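### When a partial AE onset date is ambiguous, SAP 5.1 assumes post-dose onset without checking the stop date, so an event that ended before the first infusion can be counted as a TEAE

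*SAP*

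**What the plan says.** The paragraph on missing AE dates in SAP 5.1 sets the test: "the non-missing parts of the partial dates will be used to determine if an AE occurred prior to the first dose of Replagal". The default follows, and it carries a condition: "Unless the non-missing parts are *unambiguously* before or after the first Replagal". Where the known parts leave the matter open, the outcome is fixed: "it will always be assumed that the AE occurred after the first Replagal dose". The rule refers to partial dates only and does not mention a stop date.

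SAP 5.7.1 defines the two classes that the rule feeds. On one side: "Pre-treatment AEs are any AEs that occur from the time the patient has signed informed consent until prior to the first study drug infusion". On the other, TEAEs are "those events that occurred or worsened in severity after first treatment with Replagal AF until 30 days after the last dose".

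Pre-dose events can be in the data. Protocol 6.10.4.1 runs AE observation from the time the patient "gives informed consent until the patient's final evaluation of the study", and SAP 5.1 lets the screening period reach back up to 6 months before the first dose. SAP 7.2 exempts partial dates from its no-imputation rule but adds no stop-date step, and neither does Protocol 7.5.

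**The concern.** A worst-case default is sound when the timing of an event is unknown. If a recorded stop date falls before the first infusion, the timing is known: the event ended before any study drug was given in this protocol, so it can neither have occurred nor have worsened after treatment. Applied literally, the rule replaces that fact with an assumption and conflicts with both definitions in SAP 5.7.1.

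The affected output is the TEAE tables by system organ class and preferred term, with their severity and relationship breakdowns. Safety is the study's only objective and there is no comparator arm. The by-patient AE listing could also show a treatment-emergent flag beside a stop date earlier than the first dose.

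**Working it through.** The plan gives no figure on this point. Its one design figure (SAP 3.6) is 60 patients, a 5% event frequency and at least a 95% chance of seeing one event. It reproduces as 1 − 0.95^60 = 0.954 and is not affected.

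**The rule on single cases.** First dose is read as the first study drug infusion, here 20 March 2012.
- Onset in March 2012, day unknown; stop date 10 March 2012. The known parts (March 2012) could be before or after 20 March, so the default applies and the event is a TEAE. It ended 10 days before dosing, so by SAP 5.7.1 it is pre-treatment.
- Onset in February 2012, day unknown. The known parts are clearly before the first dose, so the event is correctly not a TEAE.

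**How often the default catches an event that ended before dosing.** The rule was applied to an enumerated set. The assumptions, none of them from the documents, are: onset 1 to 183 days before the first dose, each equally likely; durations of 0, 3, 7, 14 and 30 days; first dose on each of 365 consecutive days from 1 January 2012; a complete stop date before the first dose. For each first-dose day the combinations that end before dosing number 183 + 180 + 176 + 169 + 153 = 861, and 861 × 365 = 314,265 events. The numbers flagged as TEAE are:
- complete onset date: 0 (0%)
- day missing: 14,392 (4.6%)
- day and month missing: 230,689 (73.4%)
- onset wholly missing: 314,265 (100%), if the rule is extended to that case, which SAP 5.1 does not expressly cover

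These are shares of events that already have the stated type of missing date. They are not shares of all AEs.

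**With a stop-date check added.** The number flagged falls to 0 in every row. All 184 × 5 × 365 = 335,800 enumerated events with onset on or after the first dose stay treatment-emergent. Both results follow directly from assuming that recorded stop dates are correct.

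**Illustrative count in the study.** Expected false TEAEs = N × AE rate per patient-month × pre-dose months in the first-dose month × share lacking the onset day × share resolved before dosing. Assumed inputs: 0.2 to 0.5 AEs per patient-month, 0.5 month, 5% to 15%, and one half.
- N = 60: 60 × 0.2 × 0.5 × 0.05 × 0.5 = 0.15, up to 60 × 0.5 × 0.5 × 0.15 × 0.5 = 1.125
- N = 200: 0.5 to 3.75

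For scale, 60 patients over 24 months (the follow-up used for the interim analysis in SAP 7.3) at the same rates give 60 × 24 × 0.2 = 288 to 60 × 24 × 0.5 = 720 AEs. The false TEAEs are then 0.15/288 = 0.05% to 1.125/720 = 0.16% of them.

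Two simplifications push the count up: every patient gets half a month of observed pre-dose time, and there is no factor for the stop date being complete. One pushes it down: onset dates with only the year known are left out.

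**The case against.** The best case for the plan is that the SAP is silent on stop dates and does not rule them out. The rule speaks of partial AE dates without saying onset, so partial stop dates arguably fall under it already. A programmer who knows the SAP 5.7.1 definitions might well apply a stop-date check unprompted. Derivations are to be documented in the define document and the dataset programs (SAP 5.1), all AEs are listed with TEAEs flagged (SAP 5.7.1), and data review meetings precede database lock (SAP 7.3). Post-dose default is also the cautious direction in a safety study, and no formal tests are done.

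Much of this stands as a limit on severity. It does not remove the point: the written default says always, no section states an exception, and the safeguards offer places to notice the anomaly without any instruction to correct it.

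Three stronger readings are tempting, and the documents do not support them.
- A reader might infer that any AE with a stop date before the first infusion becomes a TEAE. It does not: the default applies only when the onset is partial and its known parts are ambiguous.
- A reader might infer a visible distortion in a small Cohort 2, since one false case among 10 patients moves a preferred-term row by 10 percentage points. The size of Cohort 2 is not given, and with 10 patients assumed the formula above yields only 0.025 to 0.19 expected events.
- A reader might infer that the infusion-related reaction and drug-relatedness results are compromised. Infusion-related reactions need onset during or within 12 hours after the start of an infusion, plus judged relatedness, so they should be largely untouched. An event that ended before any study drug would ordinarily be recorded as not related.

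Pre-dose events may also be few. The schedules of events in both documents mark AE assessment only from dosing onward, even though Protocol 6.10.4.1 starts observation at consent.

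**Conclusion.** The point holds in a narrow form. For an AE with a partial, ambiguous onset date and a recorded stop date before the first infusion, SAP 5.1 as written gives a classification that SAP 5.7.1 contradicts. The direction is certain: TEAEs can only be over-counted, and no true TEAE is lost. The size cannot be derived from the documents, which give no AE rate, partial-date frequency, consent-to-dose interval or Cohort 2 size. Every count above rests on assumed inputs, and all suggest a very small effect. It also presumes that the CRF records AE stop dates, which the documents do not show. This is a minor clarification worth making before database lock. It does not threaten the study's safety conclusions.

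**What to change.** Keep the existing rule in SAP 5.1 and add one exception, for example:

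> For an AE with a partial onset date: if the AE stop date (complete, or its known parts) is unambiguously before the first study drug infusion, the AE is classified as pre-treatment. Otherwise, unless the known parts of the onset date are unambiguously before or after the first infusion, onset is taken to be after the first dose. The 30-day post-last-dose limit in Section 5.7.1 still applies.

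The opening restriction to partial onset dates and the closing sentence both matter. Without them the text could be read as covering every AE, or as making an event that starts more than 30 days after the last dose treatment-emergent. An event that stops on the day of the first infusion, or whose stop date is itself ambiguous, keeps the cautious default.

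The cost is a few lines in the SAP and one line of derivation code. The downside is that the exception trusts the stop date: if that date is wrong, a true TEAE could be moved to pre-treatment. Cases that trigger the exception should therefore be queried during data cleaning.
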